### 3.1.5 Dose Escalation

Dose escalation decisions will be based on the NCI Common Terminology Criteria for Adverse Events (CTCAE), Version 5.0 (2) and Se-Ca levels.

The DMB will review the seven-day safety data in each cohort before authorizing the initiation of the next cohort according to the following decision tree:

1. No Grade 3 AEs suspected related to study drug and no indication of effect observed from Se-Ca will result in the next dose at 3x the previous cohort dose.
2. No Grade 3 AEs suspected related to study drug and clear indication of effect on Se-Ca will result in the next dose at 2x the previous cohort dose.
3. A Grade 3 AE suspected related to study drug in a single (n=4) cohort and the absence of prohibitive effects on Se-Ca will result in an additional cohort at the same dose.
4. A single Grade 3 AE suspected related to study drug in 2 cohorts at the same dose (n=8) cohort and the absence of prohibitive indication of effects on Se-Ca will result in a dose escalation to 1.5x the previous dose.
5. Two or more of the same Grade 3 AE within the same cohort suspected related to study drug, or average peak Se-Ca > 1.5 mg/dl above the Upper Limit of Normal (ULN) range will terminate dose escalation.
  - a. If the last dose escalation was 50% and by implication 2 cohorts received the previous dose for an n=8, the study will stop.
  - b. If the last dose escalation was >50%, the next cohort should receive a dose 2/3x the previous dose.

Any DMB recommendation that deviates from the decision tree will be ratified by the Sponsor prior to implementation.

The study schematic is presented in [Section 3.2](#).

[figure not shown]

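### The dose-escalation tree names only Grade 3: read literally, one related Grade 4 or 5 AE permits a 3x or 2x step, and even a generous reading does no more than repeat the dose.

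*Protocol*

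**What the plan says.** Protocol 3.1.5, repeated in the synopsis, has the DMB review seven-day data "before authorizing the initiation of the next cohort according to the following decision tree". Grading is by CTCAE version 5.0. The AE conditions are:

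- Rule 1 (next dose 3x): "No Grade 3 AEs suspected related to study drug and no indication of effect observed from Se-Ca".
- Rule 2 (next dose 2x): "No Grade 3 AEs suspected related to study drug and clear indication of effect on Se-Ca".
- Rule 3 (repeat the dose, if calcium is not prohibitive): "A Grade 3 AE suspected related to study drug in a single (n=4) cohort".
- Rule 4 (1.5x, if calcium is not prohibitive): "A single Grade 3 AE suspected related to study drug in 2 cohorts at the same dose (n=8) cohort".
- Rule 5 (end escalation): "Two or more of the same Grade 3 AE within the same cohort suspected related to study drug", or average peak Se-Ca more than 1.5 mg/dl above ULN. Rule 5a adds "If the last dose escalation was 50% and by implication 2 cohorts received the previous dose for an n=8, the study will stop". Under 5b, after a larger step, "the next cohort should receive a dose 2/3x the previous dose".

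Neither copy of the tree says that Grade 3 includes higher grades, and neither mentions Grade 4 or 5. A DMB recommendation outside the tree needs Sponsor ratification.

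**The concern.** An escalation rule should never respond less cautiously to a worse event. Here the two rules that raise the dose most are conditioned on the absence of Grade 3 events, so a related Grade 4 or 5 event does not block them. The more serious event then leads to the higher next dose.

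Reading Grade 3 as Grade 3 or higher removes that reversal but leaves a second gap. The tree has no hold or stop for a single life-threatening or fatal event judged related to study drug. At stake is the written default for the next cohort of healthy volunteers in a first-in-human study.

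**Working it through.** **Inputs.** Starting dose 4 µg (Protocol 3.1.2); cohorts of 4 (3.1.1); step factors 3, 2, 1, 1.5 and 2/3 (3.1.5). Assumptions: calcium is not prohibitive, taken as average peak Se-Ca not above ULN + 1.5 mg/dl; where two AEs occur, they are the same AE. The plan states no figure on this point to reproduce.

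**Step 1. Apply the tree to a first cohort of four at a dose, under both readings.**

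| Related AEs in the cohort | Exactly Grade 3 | Grade 3 or higher |
|---|---|---|
| None at Grade 3 or above | 3x or 2x | 3x or 2x |
| One Grade 3 | Repeat (rule 3) | Repeat (rule 3) |
| One Grade 4 or 5 | 3x or 2x (rule 1 or 2) | Repeat (rule 3) |
| One Grade 3 and one Grade 4 | Repeat (rule 3) | End escalation (rule 5) |
| Two Grade 3 | End escalation (rule 5) | End escalation (rule 5) |
| Two Grade 4 | 3x or 2x (rule 1 or 2) | End escalation (rule 5) |

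If calcium is prohibitive, rule 5 ends escalation whatever the AE grade.

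**Step 2. Next dose after one related AE at 4 µg, literal reading.** Grade 3: 4 × 1 = 4 µg. Grade 4 or 5: 4 × 3 = 12 µg with no calcium effect, or 4 × 2 = 8 µg with a clear one. The ratios to the Grade 3 case, 12/4 = 3 and 8/4 = 2, are simply the rule multipliers and hold at any dose.

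**Step 3. The same event if Grade 3 or higher was meant.** Rule 3 gives 4 × 1 = 4 µg again. If no further such event follows among the 8 participants, rule 4 gives 4 × 1.5 = 6 µg. Protocol 3.1.3 requires staggering only above doses already given, so the repeat cohort would have no required sentinels.

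**Step 4. Two of the same related AE at 12 µg, after a 3x step from 4 µg, literal reading.** Grade 4 gives 12 × 3 = 36 or 12 × 2 = 24 µg. The Grade 3 comparator depends on what previous dose means in rule 5b:

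- The dose just reviewed, as in rules 1, 2 and 4: 12 × 2/3 = 8 µg; ratios 36/8 = 4.5 and 24/8 = 3.
- The dose before the last step, as rule 5a uses the words: 4 × 2/3 = 2.67 µg; ratios 36/2.67 = 13.5 and 24/2.67 = 9.

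The text does not settle which applies, so these are a range. After a 1.5x step, two of the same Grade 3 AE stop the study under rule 5a, while two of the same Grade 4 AE still literally meet rule 1 or 2.

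**Step 5. Which events reach the tree.** At each new highest dose, 3.1.3 requires a 72-hour safety review after the first participant and again after the second. A Grade 4 or 5 event in either within 72 hours should halt the cohort before the Day 7 review. The exposed cases are mainly events in the last two participants, or after 72 hours. The two-event case needs both events to fall there.

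The documents give no AE rates, so no probability is stated.

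**The case against.** The strongest reply is that nobody would read the tree this way. It works as a severity threshold, and Grade 3 or higher was very probably intended. Sentinel reviews come first. SAEs reach the Sponsor within 24 hours (6.10.1.4), potential dose-limiting toxicities go to the DMB under the Safety Plan (4.3.1.3), and the Sponsor may stop the study (4.3.1.4). The DMB only recommends (7.3.1), and its further actions follow the Safety Plan (7.3.2). That plan and the figures in 3.1.5 and 3.2 could already contain the missing words.

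Most of this stands as a limit on practical risk. It does not repair the rule: nothing in the available text sets a different next dose, and the intended reading still lacks a hold or stop for one related Grade 4 or 5 event (Step 3).

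A reader might infer more than the documents support:

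- *That the trial would escalate after a Grade 4 event or a death.* The finding concerns the written default. The DMB and Sponsor can depart from it.
- *That a hold necessarily counts as a deviation needing ratification.* This is arguable, because the DMB separately authorizes each cohort and could withhold authorization without changing the tree's dose.
- *That the dose-limiting toxicity list in 3.1.4 has the same error.* Its equals sign may be a greater-or-equal sign garbled in the PDF reading, so it is not counted.
- *That the two-event ratios are fixed at 4.5 and 3.* They depend on one of two readings of rule 5b.

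**Conclusion.** The point holds for the wording of the tree in both places. With calcium not prohibitive and no related Grade 3 AE, one related Grade 4 or 5 AE literally leads from 4 µg to 12 or 8 µg, against 4 µg after one related Grade 3 AE. On the intended reading the reversal disappears, but such an event only repeats the dose and may then allow 6 µg. This is a wrong stated decision rule and more than a missing detail. It should be fixed. It is not a blocking error, because sentinel review should catch early events in the first two participants and the DMB and Sponsor can act outside the tree. Confidence is high on the wording and medium for the plan as a whole, since the Safety Plan and figures were not available.

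**What to change.** In both Protocol 3.1.5 and the synopsis:

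1. Add a branch read before rules 1 to 4: any related Grade 4 or 5 AE means no escalation and no further dosing pending DMB review.
2. In rule 5, count two or more of the same AE at Grade 3 or higher, and state that rule 5 termination takes precedence over the hold in item 1. Otherwise the hold could displace the firmer outcome.
3. Optionally, for clarity, write Grade 3 or higher in rules 1 and 2. Keep rules 3 and 4 for Grade 3 only: adding the words to rule 4 would let one Grade 4 or 5 AE among 8 participants lead from 4 to 6 µg.
4. Check that the Safety Plan and the figures agree.

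Cost: items 1 and 2 are 2 × 2 = 4 text changes. The optional edits to rules 1 and 2 add 2 × 2 = 4. No extra participants or data are needed.

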### 3.1.6 Individual Participant Schedule

A screening visit will take place within 28 days of dosing. Eligible participants for each cohort will be admitted to the Clinical Research Unit (CRU) 1 day prior to dosing and remain in the CRU through at least 72 hours after dosing for safety and PK assessments before discharge. The total confinement period will be 4 nights, unless extended for management of AEs at the discretion of the Investigator. The schedule of events while

inpatient is provided in [Section 7.1.1](#). Follow-up visits to the CRU will occur on/about days 5, 7, 14, 21 and 28. Participants will be monitored closely during the duration of the study for safety, PK, and PD assessments as described in [Section 3.2](#). The total duration of follow-up period may be modified in the final study design based on safety and PK data from non-clinical studies, anticipated PK/PD response and extended in individual participants as needed to observe their calcium levels return to concentrations deemed not needing further follow up.

Additional/Alternative PK/PD time points may be implemented if the Sponsor determines this is necessary to fully characterize the PK profile of EXT608.

### 3.2 Trial schematic

### **3.3 Design rationale**

#### **3.3.1 Population**

PK modeling of various approaches to extend the half-life of compounds in animals is generally not a good predictor of half-life in humans. Knowledge of single dose PK and indications of PD in humans are usually sufficient to model multiple dose PK accurately and with reasonable precision, and can give good indications of plasma drug concentrations. This enables the accurate determination of target dose range for therapeutic effect and therefore guides optimal design choice for studies in patients with hypoparathyroidism.

The safest population in which to obtain the single dose PK is healthy participants.

#### **3.3.2 Control**

To study the PD, the most appropriate comparator is placebo, and as the participants do not have a parathyroid hormone deficiency, there are no concerns associated with that.

#### **3.3.3 Intervention**

EXT608 is the compound under development.

#### **3.3.4 Stratification, randomization and adaptive treatment allocation based on baseline covariates with strata**

In the modest planned cohort size, the DMB needs evaluable data up to and including Day 7 for a reliable dose escalation decision. Any participants for whom such data are not available will be replaced with a new participant receiving the same treatment assignment as the original participant to ensure the 3:1 ratio of active compound to control.

#### **3.3.5 Blinding**

The primary outcome is safety and tolerability. The assessment relies partly on adverse events evaluations that are prone to reporting bias and can be effectively mitigated with the double-blind design.

#### **3.3.6 Endpoint**

Dose limiting toxicity is routinely determined by AEs related to the intervention under investigation. Acute effects of parathyroid hormone analogues can be monitored by changes Se-Ca, which is tightly regulated in normal physiology with a narrow normal range. Furthermore, the relationship between elevated Se-Ca and adverse effects is well established. The combination of the limiting toxicity guided by PD therefore appears optimal in this situation.

## **4 Selection and Withdrawal of Participants**

### **4.1 Participant inclusion criteria**

Participants must meet each of the following inclusion criteria to be eligible for randomization:

1. Ability to personally provide written, signed, and dated informed consent to participate in the study.
2. An understanding, ability, and willingness to fully comply with study procedures and restrictions.
3. Male or female between 18 and 55 years of age. Male subjects with female partners of child bearing potential must agree to use barrier contraception, e.g., condoms plus spermicide, from administration of the study drug until at least 3 months after administration of the study drug. Abstinence from heterosexual intercourse from administration of study drug until at least 3 months after administration of study drug is acceptable if it is in accordance with the subject's lifestyle. Female subjects should be surgically sterile (had a bilateral tubal ligation, hysterectomy, bilateral salpingectomy, bilateral oophorectomy, or hysterectomy), postmenopausal (defined as 12 months with no menses prior to Screening and a serum follicle stimulating hormone in the postmenopausal range at Screening), or, if of child bearing potential, must be non-lactating and willing to use a highly effective method of birth control for 30 days prior to administration of study drug and agree to continued use of this method until at least 1 month after administration of study drug. Abstinence from heterosexual intercourse for 30 days prior to administration of study drug until at least 1 month after the administration of study drug is acceptable if it is in accordance with subject's lifestyle.
4. Body mass index between 18.5 and 32 kilogram per square meter ( $\text{kg}/\text{m}^2$ ), inclusive, with a body weight greater than or equal to ( $\geq$ ) 45 kg (99 pounds [lbs]). This inclusion criterion will only be assessed at the first screening visit.
5. The participant is in general good medical health with no clinically significant or relevant abnormalities, including medical history, physical exam, vital signs, ECG, and laboratory evaluations (hematology, chemistry, and urinalysis) as assessed by the Investigator.
6. Willing and able to consume standardized meals during the confinement period of the study. All participants will be required to consume similar meals and amounts as practicable on study days when serial pharmacokinetic (PK) and pharmacodynamic (PD) blood samples are collected.
7. A clinical safety laboratory parameter of hemoglobin greater than ( $>$ ) 11.7 gram per deciliter (g/dl) (females) or 13.1 g/dl (males) and less than ( $<$ ) 16 g/dl (females) or 17.4 g/dl (males) or, if out of this range, deemed not clinically significant by the Investigator.
8. Total Se-Ca within laboratory normal limits.
9. Serum parathyroid hormone (PTH) concentration within normal laboratory limits.

## 4.2 Participant exclusion criteria

Participants are excluded from the study if any of the following exclusion criteria are met:

1. Participant has received any investigational compound within 30 days prior to the first dose of study product, or within 5 half-lives, whichever is greater.

2. Participant is a study site employee or an immediate family member of a study site employee.
3. Participant has evidence of clinically significant (CS) neurologic, cardiovascular, pulmonary, hepatic, hematopoietic disease, renal, metabolic, gastrointestinal, urologic, immunologic, endocrine disease, serious allergy, allergic skin rash, psychiatric disorder, or other abnormality that may impact the ability of the participant to participate or potentially confound the study results.
4. There is any finding in the participant's medical history, physical exam, or safety laboratory tests giving reasonable suspicion of a disease that would contraindicate taking EXT608, or a similar drug in the same class, or that might interfere with the conduct of the study.
5. Participant has a known hypersensitivity to any component of the formulation of EXT608.
6. Participant has a positive urine result for drugs of abuse at Screening or Inpatient Check-in (Day -1).
7. Participant has a history of drug abuse (defined as any illicit drug use) or alcohol abuse within 1 year prior to the Screening Visit or is unwilling to agree to abstain from alcohol and drugs throughout the study.
8. Participant is currently using any medication (including over-the-counter [OTC], herbal or homeopathic preparations), that, in the opinion of the Investigator, cannot be discontinued and avoided for 4 weeks (or other time period as noted below) prior to the first dose through 1 month after dose administration.  
Specifically:
  - a. 14 days - thiazide diuretics
  - b. 30 days - loop diuretics, lithium, systemic corticosteroids (medical judgment is required by the Investigator). Primarily high doses of systemic corticosteroids (i.e. prednisone) should be excluded
  - c. 3 months - calcitonin, cinacalcet hydrochloride, treatment with rhPTH (1-84) or N-terminal PTH or PTH-related peptide fragments or analogs
  - d. For females: changes in hormone replacement therapy within 3 months are excluded. Stable ( $\geq 3$  months) hormone replacement therapy is acceptable
  - e. 6 months - fluoride tablets, oral bisphosphonates, methotrexate, growth hormone, digoxin, raloxifene or similar selective estrogen receptor modulators (SERMs)
  - f. 12 months - intravenous bisphosphonates
9. Participant is pregnant, nursing, or planning a pregnancy during the course of or within 3 months of completing this study.
10. Participant is male and intends to donate sperm before 90 days after study drug administration.
11. Participant has a history of cancer or other malignancy, with the exception of basal cell carcinoma that has been in remission for at least 5 years prior to Day -1.
12. Participant has a positive test result for hepatitis B surface antigen (HBsAg), hepatitis C virus (HCV) antibody or a human immunodeficiency virus (HIV) infection at Screening.
13. Participant has used nicotine-containing products (including but not limited to cigarettes, electronic cigarettes, pipes, cigars, chewing tobacco, nicotine patch or

nicotine gum) within 28 days prior to Inpatient Check-in (Day -1) or a positive urine cotinine test at Screening or Inpatient Check-in (Day -1).

14. Participant has poor peripheral venous access.
15. Participant has donated or lost 450 mL or more of their blood volume (including plasmapheresis) or had a transfusion of any blood product, within 45 days prior to Day 0.
16. Participant has a Screening or Inpatient Check-in (Day -1) abnormal (CS) ECG.  
Entry of any participant with an abnormal (NCS) ECG must be approved and documented by signature by the Investigator or medically qualified sub-investigator.
17. Participant has a resting blood pressure outside the ranges of 90 to 140 mm Hg for systolic and 55 to 90 mm Hg for diastolic, confirmed with repeat per Investigator discretion, at the Screening Visit or Inpatient Check-in (Day -1).
18. Participant has a resting heart rate outside the range 40 to 90 bpm, confirmed with repeat per Investigator discretion, at the Screening Visit or Inpatient Check-in (Day -1).
19. Participant has increased CV proarrhythmic potential (3):
  - a. Participant has a QT interval with Fridericia's correction method (QTcF) >450 ms (males) or >450 ms (females) or PR outside the range of 120 to 220 ms, confirmed with one repeat testing, at the Screening Visit or Inpatient Check-in (Day -1) Visit.
  - b. A history of additional risk factors for TdP (e.g., heart failure, hypokalemia, family history of Long QT Syndrome).
  - c. The use of concomitant medications that prolong the QT/QTc interval.
20. Participant has abnormal Screening or Inpatient Check-in (Day -1) laboratory values that suggest a CS underlying disease or participant with the following laboratory abnormalities: ALT and/or AST >1.5 the ULN, confirmed with one repeat testing.
21. Participant is at increased baseline risk for osteosarcoma such as participant with Paget's disease of bone or unexplained elevations of alkaline phosphatase, young adult participants with open epiphyses, participants with hereditary disorders predisposing to osteosarcoma or participant with a prior history of external beam or implant radiation therapy involving the skeleton are excluded.

### **4.3 Participant withdrawal criteria**

#### **4.3.1 Originator of withdrawal request**

##### **4.3.1.1 Participant choice**

Study participants are free to withdraw from the study at any time at their own initiative. Participants should be instructed in the importance of notifying the site of such a decision.

##### **4.3.1.2 Investigator determination**

The Investigator may withdraw the participant at his or her discretion should further participation for medical reasons not be in the participant's best interest, or for non-

compliance with the CRU rules and requirements. If possible, the Medical Monitor for the study should be contacted to discuss the individual case before withdrawal.

#### **4.3.1.3 Data Monitoring Board Recommendation**

Potential DLTs as listed in [Section 3.1.4](#) are evaluated by the DMB per the procedures outlined in the Safety Plan.

#### **4.3.1.4 Sponsor request**

The Sponsor may request discontinuation of any participant for non-compliance with study procedures or other significant protocol violations, and may discontinue the study in the case that significant new information becomes available that renders the study unsafe or of questionable medical and scientific value to continue.

### **4.3.2 Withdrawal documentation**

In case of withdrawal, the end of study Case Report Form (CRF) must be filled out including the reasons for the withdrawal, and if possible, a full end of study visit should be completed, and as a minimum the Investigator must evaluate that the participant is clinically stable for release from the study.

### **4.3.3 Follow up on withdrawn participants**

Early discontinuation does not nullify the need to follow adverse events up until resolution or stabilization.

### **4.4 Non-completer replacement policy**

Any participants who do not complete and deliver data for a reliable Day 7 assessment for review by the DMB for dose escalation decisions will be replaced with a new participant receiving the same treatment assignment as the original participant after discussion and approval by the Sponsor's Medical Monitor.

## **5 Treatment of Participants**

### **5.1 Lifestyle**

Participants will be instructed to continue to lead their normal lifestyle except they should refrain from high intensity aerobic and anaerobic exercise for the duration of the study.

### **5.2 Concomitant medications**

#### **5.2.1 Medications for the investigated condition**

Not applicable.

#### **5.2.2 Other concomitant medications and dietary supplements**

Except as noted in [Section 5.2.3](#), and [Section 4.2](#) (Exclusion criterion #8) all medication and dietary supplements should be discontinued at least 4 weeks prior to investigational product dosing, and if possible, no new medications should be started. If any changes of

products or doses occur, the Investigator must be notified by the participant to ensure adequate documentation.

